2.4.34 Changes in Laboratory Test Values (Glucose Metabolism)

Statistical Analysis Set	Safety-evaluable patients in this special drug use surveillance
Details of Statistical Analysis	Calculate summary statistics at each evaluation timepoint for fasting blood glucose (mg/dL) and HbA1c (NGSP value) (%) measurements and variations from baseline. In addition, calculate the 95% confidence interval for the mean value for variations from baseline.
Figure/Table No.	Table 2.4.34

2.4.35 Changes in Laboratory Test Values (Glucose Metabolism) <With Diabetic Complications>

Statistical Analysis Set	Safety-evaluable patients in this special drug use surveillance
Details of Statistical Analysis	Calculate summary statistics at each evaluation timepoint for fasting blood glucose (mg/dL) and HbA1c (NGSP value) (%) measurements and variations from baseline. In addition, calculate the 95% confidence interval for the mean value for variations from baseline.
Remarks	Stratification factor: With diabetic complications
Figure/Table No.	Table 2.4.35

2.4.36 Changes in Laboratory Test Values (Glucose Metabolism) <Without Diabetic Complications>

Statistical Analysis Set	Safety-evaluable patients in this special drug use surveillance
Details of Statistical Analysis	Calculate summary statistics at each evaluation timepoint for fasting blood glucose (mg/dL) and HbA1c (NGSP value) (%) measurements and variations from baseline. In addition, calculate the 95% confidence interval for the mean value for variations from baseline.
Remarks	Stratification factor: Without diabetic complications
Figure/Table No.	Table 2.4.36

2.4.37 Summary of Onset Status of Serious Adverse Events (Exhibit 2-2)

Statistical Analysis Set	Safety-evaluable patients in clinical studies before approval (total of patients in clinical studies in Japan used for safety evaluation stated in the Adverse Drug Reactions section of the package insert) and this special drug use surveillance												
Details of Statistical Analysis	
Compile the following items per survey unit period of the prior-approval status and of the special drug use surveillance.
 
Statistical analysis of ‘number of study sites,’ ‘number of surveyed patients,’ ‘number of patients,’ and ‘number of SAEs’ should cover safety-evaluable patients locked during each survey unit period.
 
  
 Item Name	Details of Statistical Analysis	
   
 Number of study sites	Number of medical institutions that have collected eCRFs	
 
 Number of surveyed patients	Number of safety-evaluable patients.	
 
 Number of patients	Number of patients with SAEs	
 
 Number of SAEs	Number of SAEs Every PT occurring should be counted as one event.	
 
 Rate of patients	Calculated by the following equation: [Number of Patients with SAEs] / [Number of Safety-Evaluable Patients] × 100.	
  
 
SAE type
 
The calculation method in performing each analysis should be as follows:
 
[Number of patients with SAEs]
 
 • Number of patients in which SAEs occurred. 
[Number of SAEs]
 
 • Number of SAEs that occurred. If the same SAE occurs more than once in the same patient, a total of frequencies of the SAE should be counted. 
[Rate of patients with SAEs]
 
 • Calculated by the following equation: [Number of Patients with SAEs] / [Number of Safety-Evaluable Patients] × 100. 
[SAE type]
 
 • SAEs should be replaced by MedDRA terms. Categorize by SOC and compile SAEs by PT in each category. If SOC is ‘Investigations,’ classify by HLG (sort by HLG code in ascending order but without outputting) and compile SAEs by PT. 
 • At SOC level, the numbers and rates of patients with SAEs should be presented by SOC internationally agreed order. If the same SOC occurs more than once in the same patient, SAEs should be counted as one patient in the SOC. 
At PT level, the numbers and rates of patients with SAEs should be presented by PT code in ascending order. If the same PT occurs more than once in the same patient, SAEs should be counted as one patient in the PT.
	Item Name	Details of Statistical Analysis	Number of study sites	Number of medical institutions that have collected eCRFs	Number of surveyed patients	Number of safety-evaluable patients.	Number of patients	Number of patients with SAEs	Number of SAEs	Number of SAEs Every PT occurring should be counted as one event.	Rate of patients	Calculated by the following equation: [Number of Patients with SAEs] / [Number of Safety-Evaluable Patients] × 100.
Item Name	Details of Statistical Analysis												
Number of study sites	Number of medical institutions that have collected eCRFs												
Number of surveyed patients	Number of safety-evaluable patients.												
Number of patients	Number of patients with SAEs												
Number of SAEs	Number of SAEs Every PT occurring should be counted as one event.												
Rate of patients	Calculated by the following equation: [Number of Patients with SAEs] / [Number of Safety-Evaluable Patients] × 100.												

		The number of SAEs of which causal relationship to the Drug has been denied should be entered in the [] brackets. In that case, if the same PT events which are both "related" and "not related" in causality to the Drug occur in the same patient, the SAEs should be counted as one patient in the "related" category.
	Cumulative total of special drug use surveillance	A respective total of the numbers of study sites and patients per survey unit period. Do not double-count the same medical institution when counting the number of study sites.
Figure/Table No.	Table 2.4.37	

2.4.38 Summary of Onset Status of Serious Adverse Drug Reactions or Infections

Statistical Analysis Set	Safety-evaluable patients in this special drug use surveillance	
Details of Statistical Analysis	Compile the following items.	
	Item Name	Details of Statistical Analysis
	Number of study sites	Number of medical institutions that have collected eCRFs
	Number of surveyed patients	Number of safety-evaluable patients.
	Number of patients	Number of patients with serious ADRs
	Number of serious ADRs	Number of serious ADRs Every PT occurring should be counted as one event.
	Rate of patients	Calculated by the following equation: $[\text{Number of Patients with serious ADRs}] / [\text{Number of Safety-Evaluable Patients}] \times 100$.
	Serious ADR type	
The calculation method in performing each analysis should be as follows:
 
[Number of patients with serious ADRs]
 
 • Number of patients in which serious ADRs occurred. 
[Number of serious ADRs]
 
 • Number of serious ADRs that occurred. If the same serious ADR occurs more than once in the same patient, a total of frequencies of the serious ADR should be counted. 
[Rate of patients with serious ADRs]
 
 • Calculated by the following equation: $[\text{Number of Patients with serious ADRs}] / [\text{Number of Safety-Evaluable Patients}] \times 100$. 
[Serious ADR type]
 
 • Serious ADRs should be replaced by MedDRA terms. Categorize by SOC and compile serious ADRs by PT in each category. If SOC is ‘Investigations,’ classify by HLG T (sort by HLG T code in ascending order but without outputting) and compile serious ADRs by PT. 
 • At SOC level, the numbers and rates of patients with serious ADRs should be presented by SOC internationally agreed order. If the same SOC occurs more than once in the same patient, serious ADRs should be counted as one patient in the SOC. 
At PT level, the numbers and rates of patients with serious ADRs should be presented by PT code in ascending order. If the same PT occurs more than once in the same patient, serious ADRs should be counted as one patient in the PT.
 
The number of serious ADRs of which causal relationship to the Drug has been denied should be

		entered in the [] brackets. In that case, if the same PT events which are both "related" and "not related" in causality to the Drug occur in the same patient, the SAEs should be counted as one patient in the "related" category.
Figure/Table No.	Table 2.4.38	

2.4.39 Summary of Onset Status of Serious Adverse Events in Safety-Unevaluable patients

Statistical Analysis Set	Safety-unevaluable patients in this special drug use surveillance	
Details of Statistical Analysis	Compile the following items.	
	Item Name	Details of Statistical Analysis
	Number of study sites	Number of medical institutions that have collected eCRFs
	Number of surveyed patients	Number of safety-unevaluable patients.
	Number of patients	Number of patients with SAEs
	Number of SAEs	Number of SAEs Every PT occurring should be counted as one event.
	Rate of patients	Calculated by the following equation: $[\text{Number of Patients with SAEs}] / [\text{Number of Safety-unevaluable Patients}] \times 100$.
	SAE type	
The calculation method in performing each analysis should be as follows:
 
[Number of patients with SAEs]
 
 • Number of patients in which SAEs occurred. 
[Number of SAEs]
 
 • Number of SAEs that occurred. If the same SAE occurs more than once in the same patient, a total of frequencies of the SAE should be counted. 
[SAE type]
 
 • SAEs should be replaced by MedDRA terms. Categorize by SOC and compile SAEs by PT in each category. If SOC is 'Investigations,' classify by HLGT (sort by HLGT code in ascending order but without outputting) and compile SAEs by PT. 
 • At SOC level, the numbers and rates of patients with SAEs should be presented by SOC internationally agreed order. If the same SOC occurs more than once in the same patient, SAEs should be counted as one patient in the SOC. 
At PT level, the numbers of patients with SAEs should be presented by PT code in ascending order. If the same PT occurs more than once in the same patient, SAEs should be counted as one patient in the PT.

		The number of SAEs of which causal relationship to the Drug has been denied should be entered in the [] brackets. In that case, if the same PT events which are both "related" and "not related" in causality to the Drug occur in the same patient, the SAEs should be counted as one patient in the "related" category.
Figure/Table No.	Table 2.4.39	

2.4.40 Summary of Onset Status of Serious Adverse Drug Reactions or Infections in Safety-Unevaluable patients

Statistical Analysis Set	Safety-unevaluable patients in this special drug use surveillance	
Details of Statistical Analysis	Compile the following items.	
	Item Name	Details of Statistical Analysis
	Number of study sites	Number of medical institutions that have collected eCRFs
	Number of surveyed patients	Number of safety-unevaluable patients.
	Number of patients	Number of patients with serious ADRs
	Number of serious ADRs	Number of serious ADRs Every PT occurring should be counted as one event.
	Rate of patients	Calculated by the following equation: $[\text{Number of Patients with serious ADRs}] / [\text{Number of Safety-unevaluable Patients}] \times 100$.
Serious ADR type	
The calculation method in performing each analysis should be as follows:
 
[Number of patients with serious ADRs]
 
 • Number of patients in which serious ADRs occurred. 
[Number of serious ADRs]
 
 • Number of serious ADRs that occurred. If the same serious ADR occurs more than once in the same patient, a total of frequencies of the serious ADR should be counted. 
[Serious ADR type]
 
 • Serious ADRs should be replaced by MedDRA terms. Categorize by SOC and compile serious ADRs by PT in each category. If SOC is 'Investigations,' classify by HLG (sort by HLG code in ascending order but without outputting) and compile serious ADRs by PT. 
 • At SOC level, the numbers and rates of patients with serious ADRs should be presented by SOC internationally agreed order. If the same SOC occurs more than once in the same patient, serious ADRs should be counted as one patient in the SOC. 
At PT level, the numbers of patients with serious
	

		
ADRs should be presented by PT code in ascending order. If the same PT occurs more than once in the same patient, serious ADRs should be counted as one patient in the PT.
 
The number of serious ADRs of which causal relationship to the Drug has been denied should be entered in the [] brackets. In that case, if the same PT events which are both "related" and "not related" in causality to the Drug occur in the same patient, the serious ADRs should be counted as one patient in the "related" category.

Figure/Table No.	Table 2.4.40	

2.5 Efficacy Statistical Analysis

2.5.1 Changes in Laboratory Test Values (Fasting Lipid)

Statistical Analysis Set	Efficacy-evaluable patients in this special drug use surveillance
Details of Statistical Analysis	Calculate summary statistics at each evaluation timepoint for fasting measurements and rates of change from baseline (%) of triglyceride (mg/dL), LDL cholesterol (Friedewald formula) (mg/dL), VLDL cholesterol (mg/dL), VLDL cholesterol (%), Apo-B (mg/dL), Apo-CIII (mg/dL), lipoprotein(a) (mg/dL), and remnant lipoprotein cholesterol (mg/dL). In addition, calculate the 95% confidence interval for the mean value for rates of change from baseline (%).
Figure/Table No.	Table 2.5.1

2.5.2 Changes in Laboratory Test Values (Random Lipid)

Statistical Analysis Set	Efficacy-evaluable patients in this special drug use surveillance
Details of Statistical Analysis	Calculate summary statistics at each evaluation timepoint for random measurements and rates of change from baseline (%) of triglyceride (mg/dL), VLDL cholesterol (mg/dL), VLDL cholesterol (%), Apo-B (mg/dL), Apo-CIII (mg/dL), lipoprotein(a) (mg/dL), and remnant lipoprotein cholesterol (mg/dL). In addition, calculate the 95% confidence interval for the mean value for rates of change from baseline (%).
Figure/Table No.	Table 2.5.2

2.5.3 Changes in Laboratory Test Values (Lipid)

Statistical Analysis Set	Efficacy-evaluable patients in this special drug use surveillance
Details of Statistical Analysis	Calculate summary statistics at each evaluation timepoint for random measurements and rates of change from baseline (%) of total cholesterol (mg/dL), LDL cholesterol (direct measurement) (mg/dL), HDL cholesterol (mg/dL), non-HDL cholesterol (mg/dL), Apo-AI (mg/dL). In addition, calculate the 95% confidence interval for the mean value for rates of change from baseline (%).
Figure/Table No.	Table 2.5.3

2.5.4 Changes in Fasting Lipid-Related Ratio

Statistical Analysis Set	Efficacy-evaluable patients in this special drug use surveillance
Details of Statistical Analysis	Calculate summary statistics at each evaluation timepoint for TC/HDL-C, LDL-C/HDL-C, and LDL-C/Apo-B.
Figure/Table No.	Table 2.5.4

2.5.5 Changes in Fasting Triglyceride by Patient Demographics and Treatment Details

Statistical Analysis Set	Efficacy-evaluable patients in this special drug use surveillance	
Details of Statistical Analysis	Calculate summary statistics by stratification for each item for baseline and final evaluation timepoint measurements and rates of change from baseline (%) of fasting triglyceride.	
	Item Name	Category
	Sex	Male, Female
	Age	Minimum age to 64 years, 65 to 74 years, 75 years to maximum age, Unknown
	BMI	Less than 18.5kg/m ² , 18.5 to less than 25kg/m ² , 25 to less than 30 kg/m ² , 30 kg/m ² or over, unknown
	Fasting triglyceride at baseline (mg/dL)	Less than 150 mg/dL, 150 to less than 400 mg/dL, 400 to less than 500 mg/dL, 500 to less than 750 mg/dL, 750 mg/dL or over, Unknown
	Disease duration	Less than 1 year, 1 to less than 3 years, 3 to less than 5 years, 5 years or over, Unknown
	Initial dose	2 g, 4 g, other
	Change in daily dose	No, Yes
	Breakdown of change in daily dose	2 g → 4 g, 4 g → 2 g, Other
	Mean daily dose	Less than 2 g, 2 to less than 4 g, 4 to less than 6 g, 6 g or over
	Treatment duration	1 to 30 days, 31 to 90 days, 91 to 180 days, 181 to 360 days, 361 days or over
	Presence or absence of concomitant antihyperlipidemic drug use (during observation period)	No, Yes
	Breakdown of concomitant antihyperlipidemic drugs (during	Statins drugs, Fibrate drugs, Intestinal transporter inhibitors, Anion-exchange resin, Nicotinic acid derivatives, Probucol, Ethyl icosapentate (EPA), Others

	observation period)	
Figure/Table No.	Table 2.5.5	

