9.3 Treatment Information

1) Survey items

Administration of the Drug (daily dose, treatment duration, and status of completion of treatment with the Drug), administration of antihyperlipidemic drugs other than the Drug* (presence or absence, drug name, daily dose, and treatment duration), and administration of concomitant medications (other than antihyperlipidemic drugs) (presence or absence, drug name, and purpose of administration)

*: Including antihyperlipidemic drugs with which treatment is discontinued within two months before baseline.

2) Survey timing

Period from baseline to Month 12 (or discontinuation of treatment)

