10.5.2 Factors Likely to Affect Efficacy

Compile TG values by stratification variables: patient baseline characteristics (sex and age) and treatment regimen (administration of the Drug, administration of concomitant medications, etc.).

[figure not shown]

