End date	
The end date of last administration of the Drug stated in the Treatment Duration field of the eCRF.
 
However, if the end date of last administration is in ‘ongoing 12 months after

Item	Definition
	baseline,' the end date should be the start date plus 405 days.
Observation period (in days)	Refers to the entire period of observation. The start date and end date of observation period should be the same as the 'start date' and 'end date,' respectively. Calculated by the following equation: [End Date] - [Start Date] + 1.
Treatment duration (in days)	Refers to the entire period of treatment. A total of Drug dosing periods in the number of actual administration days, excluding washout period. Calculated as a total of ([End Date] - [Start Date] + 1) in the number of actual administration days, excluding washout period.
Mean daily dose	Calculated by the following equation: Total of ([Daily Dose] × [Total Period of Treatment with the Dose]) / [Observation Period]. See the above for calculation of observation period.
Concomitant medication	A drug used during the surveillance period. However, concomitant medications exclude drugs used for adverse events occurring during the period.
Antihyperlipidemic drug	A drug starting with any of the following drug codes: 218, 2190006, 2190101, 2190102, 2190103, 2190104, 290006, 3133001, 3133400, 3399004.
Statins drug	A drug starting with any of the following drug codes: 2189010, 2189011, 2189012, 2189015, 2189016, 2189017.
Fibrate drug	A drug starting with drug code: 2183.
Intestinal transporter inhibitor	A drug starting with drug code: 2189018.
Anion-exchange resin	A drug starting with any of the following drug codes: 2189009, 2189014.
Nicotinic acid derivative	A drug starting with any of the following drug codes: 2189004, 2189005, 2190006.
Probucol	A drug starting with drug code: 2189008.
Ethyl icosapentate (EPA)	A drug starting with drug code: 3399004.
Anticoagulant drug	A drug starting with any of the following drug codes: 333, 2190408, 6343424.
Antiplatelet drug	A drug starting with any of the following drug codes: 3399 (excluding 3399004), 2171010, 2171402.
Anticoagulant/antiplatelet drug	A drug that falls under the class of either anticoagulant or antiplatelet drugs

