1.4 Handling of Evaluation Timepoint Data

The evaluation timepoints are the start of treatment with the Drug (baseline), Month 3, Month 6, Month 9, Month 12, and final evaluation timepoint.

If multiple data exist within each evaluation timepoint, calculate absolute values of difference in measurement intervals from the basic day count and adopt the minimum absolute value as date for that evaluation timepoint. If all the absolute values are the same, adopt one for the latest date of testing/measurement. Test/Measurement values should not be adopted that have been obtained after completion of treatment with the Drug. The final evaluation timepoint test/measurement should be one taken on the latest date within 405 days elapsed since the start date (including values tested/measured during washout period). Note that the number days elapsed since the start date should be counted with the start date as day 0 and the previous day as day -1.

Evaluation Timepoint	Tolerance (Number of Days Since Baseline)	Basic Day Count
Baseline	-90 to 0	0
Month 3	1 to 135	90
Month 6	136 to 225	180
Month 9	226 to 315	270
Month 12	316 to 405	360
Final evaluation timepoint	1 to 405	–

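### The triglyceride tables by concomitant lipid-drug use (SAP 2.5.5 and 2.5.6) pool unchanged background therapy with drugs started, increased, stopped or reduced after the baseline test

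*SAP*

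**What the plan says.** Section numbers here are those of the current SAP; in the superseded Ver. 3.0 the corresponding tables are 2.5.4 and 2.5.5.

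- **Outcome.** SAP 2.5.5 asks for summary statistics of "baseline and final evaluation timepoint measurements and rates of change from baseline (%) of fasting triglyceride". SAP 2.5.6 repeats this for random TG.
- **Stratifier.** One item is "Presence or absence of concomitant antihyperlipidemic drug use (during observation period", with categories No and Yes. The next item breaks use down by class (statins, fibrates, EPA and so on). This carries out Protocol 10.5.2, which names "treatment regimen (administration of the Drug, administration of concomitant medications, etc" as a stratifier and gives no timing rule.
- **What counts as concomitant.** SAP 1.1 defines it as "A drug used during the surveillance period", leaving out drugs given for adverse events. There is no condition on when the drug began or whether its dose was stable.
- **Which TG value.** SAP 1.4 takes baseline from day -90 to day 0. For the end value it says "The final evaluation timepoint test/measurement should be one taken on the latest date within 405 days elapsed since the start date". Values after the Drug is finished are not used, but a change in another lipid drug triggers no cut-off.
- **What is collected.** For other lipid drugs, Protocol 9.3 records "presence or absence, drug name, daily dose, and treatment duration", and its footnote adds "Including antihyperlipidemic drugs with which treatment is discontinued within two months before baseline".

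**The concern.** Two quite different patients fall in the same Yes group. One takes the same statin before and throughout the survey. The other has a fibrate added at month 6. In the first, background therapy is present in both TG values and largely cancels out of the change. In the second, only the final value carries the fibrate, so the change combines two drugs. A third patient, who stops a background drug after baseline, has a change that understates what happened on the Drug.

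Membership of the group is also settled after baseline. A high TG on treatment may itself prompt an addition, and a drug begun after the last TG test still makes the patient a Yes.

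The tables serve a protocol section on factors likely to affect efficacy, so a reader will naturally compare Yes with No to see how co-therapy matters. As laid out, that comparison cannot separate co-therapy that was already running from co-therapy that changed. The SAP does make this distinction for the Drug itself, with rows for 2 g to 4 g and 4 g to 2 g, but has no counterpart for other lipid drugs.

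**Working it through.** The documents state no expected TG change, no effect for any other lipid drug and no share of patients changing therapy. There is no planned figure to reproduce, and everything below is illustrative.

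**Inputs (all assumed).** rD is the ratio of final to baseline TG on the Drug alone; rA is the further ratio from an added drug; f is the share of the Yes stratum that adds a drug after the baseline test.

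**Additions.** Mean change in the pooled stratum = (1 - f)(rD - 1) + f(rD × rA - 1). The shift caused by pooling is f × rD × (rA - 1).

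With rD = 0.80 and rA = 0.70, patients without an addition show -20% and those with one show 0.80 × 0.70 - 1 = -44%. The pooled stratum reads:

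- f = 5%: 0.95 × (-20) + 0.05 × (-44) = -21.2%
- f = 10%: 0.90 × (-20) + 0.10 × (-44) = -22.4%
- f = 20%: 0.80 × (-20) + 0.20 × (-44) = -24.8%
- f = 30%: 0.70 × (-20) + 0.30 × (-44) = -27.2%

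Keeping rD = 0.80 but letting f run from 5% to 50% and the added effect from -10% to -40%, the shift runs from 0.05 × 0.80 × (-0.10) = -0.4 points to 0.50 × 0.80 × (-0.40) = -16.0 points. At f = 0 it is zero.

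**Additions in non-responders.** The formula above gives everyone the same response to the Drug. Suppose instead that the 20% who add a drug had no response to the Drug and then fall 30%. The stratum reads 0.80 × (-20) + 0.20 × (-30) = -22%. On the Drug alone it would have read 0.80 × (-20) + 0.20 × 0 = -16%. The shift is 6 points, against 4.8 under equal response.

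**Stops.** If a share g stops a background drug of ratio rB after the baseline test, their change is rD / rB - 1. With rD = 0.80 and g = 20%:

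- rB = 0.90: 0.80 × (-20) + 0.20 × (-11.1) = -18.2%
- rB = 0.70: 0.80 × (-20) + 0.20 × (+14.3) = -13.1%
- rB = 0.60: 0.80 × (-20) + 0.20 × (+33.3) = -9.3%

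So the sign of the distortion depends on whether additions or stops dominate.

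**After splitting.** In the 20% addition case, the single figure of -24.8% separates into -20.0% for unchanged background therapy and -44.0% for those who added a drug.

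**The case against.** A reader might infer that the SAP credits an added drug's effect to the Drug and so overstates efficacy. The documents do not support that reading. SAP 2.5.5 and 2.5.6 ask only for summary statistics by stratum, with no test, no contrast and no confidence interval. The objective is use in routine practice, where changes in co-therapy are part of what is described. Any attribution is the reader's, and stops push the figure the other way.

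Some mitigation is already in the plan. The class rows put a statin user and a fibrate user in different lines. The No stratum contains no lipid drug added during observation. SAP 2.5.1 and 2.5.2 report each evaluation timepoint, so values that precede a later addition remain visible.

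These points lower the stakes but do not remove the problem. The class rows show which drug was used, not when, and nothing makes them exclusive: a patient on a long-standing statin with an added fibrate belongs in both. The No stratum can include patients who stopped a lipid drug shortly before starting the Drug, possibly after their baseline TG test. The timepoint tables are not split by co-therapy at all.

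It is also fair to object that the illustrated size rests wholly on assumption. At 5% to 10% additions the shift is only 1.2 to 2.4 points.

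**Conclusion.** The point stands as a limitation of two descriptive tables. The Yes stratum and its class rows mix unchanged background therapy with therapy that changed after the baseline TG test, so the TG change shown there can include the effect of other drugs. Neither direction nor size follows from the documents. The figures of -21.2% to -27.2% hold only for an assumed Drug effect of -20%, an added-drug effect of -30% and 5% to 30% additions; they are not estimates for this survey. No test or primary conclusion depends on these rows. The change is worth making because the information is already collected and the tables cannot otherwise answer the question that Protocol 10.5.2 puts to them.

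**What to change.** In SAP 2.5.5 and 2.5.6, replace Yes/No with four groups derived from the collected drug name, daily dose and treatment duration:

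- (a) none;
- (b) unchanged from before the date of the baseline TG test through the final TG test;
- (c) started or increased after the baseline TG test;
- (d) stopped or reduced after the baseline TG test.

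Ignore changes made after the final TG test, and state in advance how a patient who meets both (c) and (d) is counted. Apply the same split to the class rows where numbers allow.

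Key the groups on the date of the baseline TG test, not on the start date of the Drug. Baseline may come from as early as day -90, so a lipid drug begun between that test and day 0 would be labelled stable under a start-date rule although its whole effect lies inside the measured change.

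Align the terms as well. SAP 1.1 refers to the surveillance period, which Protocol 8.0 gives as calendar dates (May 2013 to May 31, 2017), while the table refers to the observation period, which is counted per patient.

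Keep SAP 2.5.1 and 2.5.2 as planned. Any table limited to values before a change in other lipid drugs should be labelled a sensitivity analysis, with the caveat that it drops later values selectively, possibly from poorer responders.

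The cost is SAP wording and one derivation, and strata become smaller. The sponsor should confirm that the treatment-duration field for other lipid drugs holds usable dates by dose. Drugs stopped more than two months before baseline are not recorded, so for the oldest baseline tests some stops will be missed.
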